In the current study, the ABC standardized version of mindfulness meditation was used, which includes 5 30-minute weekly sessions of mindfulness meditation and which has been found effective in improving stress and its responses (34). An additional 3-hour educational workshop about the intervention was provided before the actual training sessions to enhance the participants' understanding of the intervention. In the initial educational session, the principal investigator (PI) held a PowerPoint presentation for the participants in each experimental group, which included an explanation of the intervention rationale and procedures and a demonstration of the entire intervention protocol. The PI is an experienced practitioner who received stress-management training at the Psychology Department at Kent State University over 7 years ago and who has, since then, been practicing stress-management techniques, especially those used in the current study, on a daily basis. The participants were asked to briefly practice the intervention, and their performance was then evaluated by the PI to make sure that the intervention had been conducted correctly. The PI gave the participants the opportunity to ask questions during the educational session.

During the actual training sessions, the intervention was introduced to the participants in the experimental groups by the PI based on Smith's (2005) guidelines and protocols. The participants were divided into 6 groups, with 10 to 11 participants in each group. The

subgroups met separately in different classrooms, where the interventions were conducted, and provided with identical instructions. Each participant sat in a hard chair behind a desk. The classrooms had tiled floors, and the lights were dimmed during the relaxation phases and turned up when the participants were completing the study questionnaires. A trained research assistant with a master's degree in psychiatric health nursing randomly selected sessions to evaluate the delivery of the interventions using checklists produced according to Smith's protocols.

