Smith's version of the mindfulness meditation intervention was used in the current study. The participants were asked to sit upright in a comfortable position, place their feet on the floor, and quietly observe and reflect on internal and external stimuli such as breathing, thought, feeling, physical sensation, and sound, without reactions, judgments, or evaluations. They were asked to quietly attend to, note, and let go of all internal and external stimuli. They were reminded that they should not try to think about, push away, or do anything with these stimuli, and that they should not focus on figuring out the connections between the stimuli. They were asked to simply let each stimulus come and go and wait for the next stimulus. Finally, the participants were told that they should not concern themselves with distractions and that if faced with a distraction, they should note it as yet another passing stimulus (e.g., "Ah, a distraction... how interesting") (34).

Control Group

Each of the control group subgroups had 10 participants. The participants were instructed to sit with their eyes closed and relax during the intervention sessions, in order to control for the nonspecific effects of trainer interaction, social interaction, attention, environment, time, and closed eyes (35). The timings of the control group interventions were similar to those of the experimental groups, whereby if a given experimental group

intervention lasted for 30 minutes, the control group participants would be asked to sit with their eyes closed and relax for 30 minutes also.

Procedure

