First, approval from the institutional review board at JUST was obtained. After obtaining permission from the dean of the nursing college at JUST and the students' instructors, the PI visited the students in their classrooms. After the students' lecture had finished, the PI made an announcement explaining the study title and objectives and asked any students who were interested in participating to contact him either on the phone number assigned for the purposes of the study or via email. The PI arranged an initial meeting to meet with students who were interested in participating, which was to be held on another day in a private room at the university. At this meeting, the PI informed the students of the study objectives, risks, and benefits, in addition to answering the students' questions and assuring them that all collected data would be kept confidential. The students were also assured that they had the full right to refuse or discontinue participation at any time and that such refusal or discontinuation would not affect their academic achievement in any way. At the same meeting, informed consent was obtained from participants who agreed to participate and who met the eligibility criteria. After that, the participants were randomly assigned equally to the study groups using a computerized random numbers procedure carried out by a research assistant who was not involved in any other parts of the study. Finally, the dates and times of the sessions were determined.

In the 2-hour educational session, baseline measurements of the study variables were taken. Then, the PI delivered a PowerPoint presentation for the participants in each subgroup, as previously explained. At the end of the workshop, to avoid experimental contamination, the participants in each experimental group were asked not to share any information related to the intervention with the participants in the control group.

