The actual training sessions were introduced to the participants in the experimental groups by the PI based on Smith's (2005) guidelines and protocols. Based on the ABC Relaxation Theory (Smith, 1999, 2002, 2005), at least two, and preferably five, weekly sessions of actual mind-body training should be provided to evoke relaxation and optimize health (36, 37). The sessions were held in a private, quiet, comfortable, and spacious room at the university. As previously mentioned, the dependent variables were measured twice, at baseline and at the end of the intervention (i.e., In the next morning after the 5th session).

Various strategies were followed to decrease measurement errors that could potentially be affected by variations in the data collection procedure. For example, filling out the questionnaire may be stressful for some subjects, hence influencing the objective measures. Therefore, the self-report measures were completed after the physical measures were taken. Also, all of the study measures in the intervention and control groups were taken in similar conditions, including similar room temperature and environment. In addition, quiet environments were maintained, with a "Do Not Disturb" sign placed on the doors of the rooms during the interventions and data collection. The data (questionnaire and blood samples) were collected by three research assistants with at least 10 years nursing experiences who were not involved in any other parts of the study.

Statistical Analysis

Statistical analysis was conducted using SPSS software (version 25). First, the data were examined for outliers, missing data, and violations of statistical tests assumptions and managed as appropriate. Descriptive statistics were used to describe the sample. The sample and study variables were described by measures of central tendency and dispersion appropriate to the level of measurement. Initial independent t-tests and Chi-squared tests were conducted to ensure that the randomization across the covariates was successful, and one-way MANOVA was used to test the study hypotheses. Post hoc one-way ANOVAs were

run to examine if there were significant differences in each of the dependent variables between the study groups. Due to multiple testing, the p-value was adjusted by dividing the p value of .05 by 4 (i.e., the number of dependent variables), with a level of .0125 considered as the level of significance for the ANOVA tests.

References

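### Baseline is measured after randomisation and scheduling, and the plan does not say that allocation was withheld until baseline was complete

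*Combined protocol and SAP*

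**What the plan says.** The Procedure section gives the order of events. Consent is taken at an initial meeting. Next: "After that, the participants were randomly assigned equally to the study groups using a computerized random numbers procedure". Then: "Finally, the dates and times of the sessions were determined". Baseline follows: "In the 2-hour educational session, baseline measurements of the study variables were taken". Within that session, measurement comes first and teaching second: "Then, the PI delivered a PowerPoint presentation for the participants in each subgroup, as previously explained".

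The session appears to be organised by arm, though the text is not uniform. Procedure speaks of every subgroup, whereas Interventions says that the PI "held a PowerPoint presentation for the participants in each experimental group". The Control Group section describes separate subgroups: "Each of the control group subgroups had 10 participants". By the end of the workshop arm membership is treated as known, because "the participants in each experimental group were asked not to share any information related to the intervention with the participants in the control group".

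Procedure also states that the outcomes are measured only twice, at baseline and on the morning after the fifth session. Design and Participants labels the trial pre-posttest and blinded, without saying who is blinded. Statistical Analysis plans t-tests and chi-squared tests "to ensure that the randomization across the covariates was successful", then a one-way MANOVA and follow-up ANOVAs. It names no covariate and does not say whether post-test values or change scores are analysed.

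**The concern.** A baseline value is useful because allocation cannot have influenced it. Measuring before randomisation guarantees this; measuring afterwards does so only if nobody concerned knows the allocation. Here baseline comes after assignment and scheduling, no earlier measurement exists, and no sentence says that allocation was concealed until baseline was complete.

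Two of the four outcomes, MAAS and PSS, are self-reported. A student who believes that they are about to receive meditation training, or that they have missed it, may answer differently. Cortisol might also respond to anticipation. At stake are any pre-post comparison and the balance tests on self-reported characteristics.

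**Working it through.** The plan gives no figure for this effect, so there is none to reproduce. The sample size does not depend on it. The check is the order of events, then the size of the bias under stated assumptions.

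**Which variables could move**

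- Could reflect knowledge of the arm: MAAS, PSS, and the self-reported coping, sleep-quality and general-health items (Instruments). Cortisol possibly.
- Could not: fixed items such as age and gender. CRP probably not.

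**How a baseline shift reaches the treatment effect**

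Let *b* be the difference between arms in mean baseline caused by knowledge of allocation, in SD units, and *r* the within-arm pre-post correlation. Assume equal SDs at both times, no true effect, and a shift that affects baseline only. Then:

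- Post-test values only: bias = 0, because baseline is not used.
- Change score (post minus baseline): bias = 0 − *b*, so its size is *b*.
- Baseline-adjusted effect: bias = 0 − *r* × *b*, so its size is *r* × *b*.

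The values of *b* (0.1 to 0.3) and *r* (0.5 to 0.7) are assumptions. Sizes of bias in SD:

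| Assumed shift *b* | Post-test only | Change score | Adjusted, *r* = 0.5 | Adjusted, *r* = 0.7 |
|---|---|---|---|---|
| 0.1 | 0 | 0.1 | 0.05 | 0.07 |
| 0.2 | 0 | 0.2 | 0.10 | 0.14 |
| 0.3 | 0 | 0.3 | 0.15 | 0.21 |

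**Direction**

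The sign is unknown. If knowing the arm raised baseline PSS in the meditation arm, a change score would exaggerate the fall in stress there. If disappointment raised it in the control arm, a change score would hide a true effect.

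**Balance tests**

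A difference on a fixed item is due to chance or to a fault in the randomisation. On a self-reported item, knowledge of allocation is a further explanation, and the test cannot tell it from chance.

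**The case against.** The strongest reply is that the documents never say that students knew their arm when baseline was taken. Measurement precedes the presentation, so the workshop content cannot have contaminated it, and the request not to share information comes only at the end. Subgroups in the two arms are of similar size and session timings are matched, so sitting in a subgroup need not reveal the arm. Measures were taken under similar conditions in both arms, blood before questionnaires, by research assistants with no other role. Most of this stands. It makes knowledge of the arm a possibility and not a documented fact. It does not close the gap: independent collectors cannot protect self-report from a student's own knowledge, and an undefined claim of blinding does not show concealment at baseline.

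A reader might infer more than the documents support:

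- **That the planned main test is biased.** It is not, if the MANOVA uses post-test values. The adjusted-effect figures above describe an analysis that the plan does not contain.
- **That the balance check is worthless.** The plan refers to covariates, not explicitly to baseline outcomes, and the demographic items include several that knowledge of the arm cannot change.
- **That the 35% attrition measures loss before the workshop.** Sample Size Calculation does not split it by time.
- **That an earlier baseline would keep lost students in the analysis.** A student without a post-test still cannot enter a one-way MANOVA. That needs a missing-data method, which is a separate matter.

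**Conclusion.** The point holds in limited form. The order is explicit: randomisation and scheduling come first and baseline second, with no statement that allocation was withheld. The consequence is conditional. It is nil for a MANOVA on post-test values. For change scores it is the full shift (0.1 to 0.3 SD if the shift is 0.1 to 0.3 SD). For an adjusted analysis, should one be added, it is 0.05 to 0.21 SD at correlations of 0.5 to 0.7. All these sizes rest on an assumed shift, and the direction could be either. Balance tests on self-reported items also lose some of their meaning. This is worth correcting because the design is labelled pre-posttest and the remedy is cheap; it does not by itself invalidate the planned comparison.

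**What to change.** Change the Procedure so that blood samples and questionnaires are completed after consent and before the random list is run. At minimum, release allocation and subgroup schedules only after a participant's baseline is complete. Report losses between randomisation and baseline by arm.

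State in Statistical Analysis whether the MANOVA uses post-test values or change scores, since the consequence turns on it. Reconcile Interventions with Procedure on whether control subgroups attended an educational session; if they did not, say where their baseline was taken.

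The staff, samples and questionnaires stay the same. One common session is unlikely to be practical: 108 students shared by three assistants is 36 each, and 60 / 36 is about 1.7 minutes per student in the 8:30-9:30 AM window. Baseline should therefore be spread over several mornings if needed. The costs are less flexible morning scheduling and a few baseline samples from students who are then not randomised.

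The document is written in the past tense and reports reliability coefficients for the current study, so baseline may already have been collected. In that case the order cannot be changed. The report should then state who knew the allocation at baseline, give the losses by arm, and say how missing baselines were handled.

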G* Power software 3.1 was used to calculate the required sample size, given a MANOVA test, an alpha of .05, power of 0.95, number of dependent variables of 4, number of groups of 2, and effect size of 0.25 (18). A sample size of 80 was calculated, and an attrition rate of 35% was added based on a previous study with variables similar to those of the present study (27). Therefore, this resulted in a final total sample size of 108 participants.

Instruments

The study data were collected using self-reported and physical measures. For the self-reported variables, a self-report questionnaire was used. The first part of the questionnaire included questions related to the behaviors and demographic characteristics of the participants, including age, religion, gender, marital status, daily consumption of cigarettes, general health status, nutritional status, coping behaviors, and sleeping hours and quality. Meanwhile, the second part included scales used to measure trait mindfulness and perceived stress. As for the physical variables, the enzyme-linked immunosorbent assay (ELISA) procedure was used to measure serum biomarkers such as serum cortisol and serum CRP.

Trait Mindfulness. Trait mindfulness was measured using the Arabic version of the Mindful Attention Awareness Scale (MAAS) (28), which is a one-dimensional scale that includes 15 items measured on a six-point Likert-type scale ranging from 1 (almost always) to 6 (almost never). The total possible score ranges between 15 and 90, with higher scores indicating higher levels of trait mindfulness. The original scale has been shown to have strong psychometric properties when validated among college students (28). Further, the Arabic version of this scale has been shown to have excellent internal consistency and convergent validity for use among Arab populations (29). In the current study, the Cronbach's alpha for the Arabic version of the MAAS was .79, indicating good internal consistency.

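### Baseline significance tests cannot certify that randomisation succeeded; adjust the outcome tests for a fixed set of prognostic baseline variables instead

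*Combined protocol and SAP*

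**What the plan says.** The Statistical Analysis section gives the baseline tests an inferential job: "Initial independent t-tests and Chi-squared tests were conducted to ensure that the randomization across the covariates was successful". The covariates are not listed there. The nearest list is under Instruments, where the questionnaire collects "age, religion, gender, marital status, daily consumption of cigarettes, general health status, nutritional status, coping behaviors, and sleeping hours and quality". That is nine characteristics, or ten if hours and quality of sleep count separately.

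The four outcomes also have baseline values, since "the dependent variables were measured twice, at baseline and at the end of the intervention". Whether those were among the tested covariates is not stated.

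For the outcomes, "one-way MANOVA was used to test the study hypotheses", followed by one-way ANOVAs "with a level of .0125 considered as the level of significance for the ANOVA tests". No covariate or baseline term appears in either analysis, and the text does not say whether post-test or change scores are analysed.

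The Procedure section says that allocation was equal and used computer-generated random numbers, handled by an assistant with no other role. It places the baseline measurements in the educational session, after allocation.

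**The concern.** Under a sound random allocation, differences between the arms as randomised arise by chance, so the null hypothesis of a baseline test is true by design. A small p-value does not show that randomisation failed. A large one does not show balance, because it depends on sample size and takes no account of how strongly the covariate predicts the outcome.

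The balance check is also the only stated use of the covariates. Information that could sharpen the outcome comparison, and protect it against a chance imbalance in this particular trial, is spent on a question that the tests cannot answer. The plan does not say what follows a significant result, which leaves room for choosing covariates after the fact.

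**Working it through.** **The plan's own figures.** The Sample Size Calculation uses "an alpha of .05, power of 0.95, number of dependent variables of 4, number of groups of 2, and effect size of 0.25". Reading the effect size as f² = 0.25, the two-group MANOVA F test has df1 = 4, df2 = N − 5 and noncentrality 0.25 × N. N = 80 gives power 0.952, which matches the stated 80. Then 80 × 1.35 = 108, or 54 per arm, and .05/4 = .0125. All three reproduce. The plan states no figure for the baseline tests.

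**Assumptions not in the documents.** Two-sided .05 for each baseline test, unadjusted; the number of tests; the correlation among tests; and the correlation r between a baseline covariate and an outcome (0.3, 0.5 and 0.7 shown).

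**1. False flags under sound randomisation.** For m independent tests, P(at least one p < .05) = 1 − 0.95^m.
- m = 9: 37%
- m = 10: 40%
- m = 14 (adding the four baseline outcomes): 51%

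With equally correlated test statistics, the figures for m = 10 and m = 14 are:
- correlation 0.1: 39% and 50%
- correlation 0.3: 35% and 44%
- correlation 0.5: 29% and 35%

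The range for 10 to 14 tests is therefore about 29–51%. Nine tests at correlation 0.5 would take the lower end to about 27%. Chi-squared tests on very rare categories lower it further: at 2% prevalence and 54 per arm, such a test rejects about 1.6% of the time.

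**2. Imbalances that pass.** The largest non-significant standardised difference is t(.975, 2n − 2) × √(2/n).
- n = 54 per arm: 1.983 × 0.1925 = 0.38 SD
- n = 40 per arm (the calculated 80): 1.991 × 0.2236 = 0.45 SD

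The power to detect a true 0.3 SD difference is 34% at 54 per arm and 27% at 40 per arm.

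**3. Effect on an unadjusted post-test comparison, given d = 0.38 at 54 per arm.** Shift = r × d. With se = √(2/54) = 0.1925 and z = 2.498 for two-sided .0125, the conditional error is approximately

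1 − Φ[(z·se − r·d)/(se·√(1 − r²))] + Φ[(−z·se − r·d)/(se·√(1 − r²))].

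For r = 0.5 the first term is 1 − Φ[(0.481 − 0.191)/0.167] = 1 − Φ(1.74) = 0.041, and the second is negligible.

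| r | Shift (SD) | Error, normal formula | Error, simulated with t critical value |
|---|---|---|---|
| 0.3 | 0.11 | 0.024 | 0.023 |
| 0.5 | 0.19 | 0.041 | 0.039 |
| 0.7 | 0.27 | 0.060 | 0.058 |

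The last column is the one to use.

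**4. Typical rather than extreme imbalance.** The median chance imbalance is 0.6745 × 0.1925 = 0.13 SD. At r = 0.5 the same formula gives about 0.007, below .0125.

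**5. Error over repeated randomisations.** The simulated level of the unadjusted test is 5.0% against 5%. Among trials with a non-significant baseline test, at r = 0.5, it is about 4.3% against 5% and about 1.0% against 1.25%.

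**6. Change scores.** If change scores are analysed and the baseline and post-test SDs are equal, an imbalance d in a baseline outcome shifts the result by (r − 1) × d. For d = 0.38 this is −0.27, −0.19 and −0.11 SD at r = 0.3, 0.5 and 0.7, opposite in direction to the post-test shift.

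**7. Effect of adjustment.** Adjusting for the covariate whatever its imbalance returns the conditional error to nominal. It also multiplies the residual variance by 1 − r²: 0.91, 0.75 and 0.51.

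**The case against.** The strongest reply is that nothing in the outcome analysis depends on these tests. The plan gives no alpha for them, no pass mark and no consequence, and the MANOVA is named unconditionally in the same sentence. Deleting the tests would leave every outcome estimate and p-value unchanged. This stands: the text describes a check and not a decision rule.

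A reader might infer three stronger things, and the documents support none of them:
- **That the outcome tests are biased.** They are not. Over repeated randomisations they keep their level, and after a non-significant baseline test they are slightly conservative. The inflated errors hold only conditional on an imbalance at the edge of significance in a prognostic covariate.
- **That a sound trial would be flagged 40–50% of the time.** That requires 10 to 14 nearly independent tests at .05. The level and number of tests are unstated, and independence is doubtful for health, nutrition, sleep and coping.
- **That a pass is used to justify the unadjusted analysis.** The plan does not say so.

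It is also fair to say that baseline was measured after allocation, so a difference could reflect loss or awareness of group before measurement. A comparison might hint at that, but a non-significant result still could not certify randomisation.

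**Conclusion.** The point holds in a limited form. The inference drawn from the baseline tests is wrong under any plausible number or correlation of tests: false flags would be common, and imbalances of about 0.4 SD would go unremarked. The tests as such do not damage the outcome results. What matters in practice is the missing baseline adjustment, which leaves conditional error exposed to a chance imbalance and gives up precision.

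The size of that exposure rests on assumed correlations of 0.3 to 0.7, on a just-passing imbalance as the worst case, and on post-test scores being analysed. Change scores, which the documents neither state nor exclude, would not remove it for an imbalance in a baseline outcome; they would reverse its direction.

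**What to change.** 1. Remove the baseline t-tests and chi-squared tests, and the claim that they show randomisation succeeded. Describe baseline characteristics by arm without p-values.
2. Replace the unadjusted one-way MANOVA and ANOVAs with MANCOVA/ANCOVA adjusted for a fixed set of prognostic baseline variables already collected. Start with the baseline value of each outcome. Add others, such as gender or daily cigarettes, only if justified on prognostic grounds. Use the set whatever imbalance is observed.
3. State which form of the outcome (post-test or change) is the dependent variable.
4. The text is written in the past tense. If the covariate set is chosen after the data were seen, label the adjusted analysis accordingly.

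The cost is a little more analysis work and a few degrees of freedom: four baseline outcomes in the MANCOVA would take df2 from N − 5 to N − 9, for example from 75 to 71 at N = 80. No new data or participants are needed.

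### With 35% attrition planned for, the stated MANOVA and ANOVAs use no baseline values and default to complete cases, leaving the comparison open to dropout that differs by arm

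*Combined protocol and SAP*

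**What the plan says.** - **Expected loss.** Under Sample Size Calculation, "A sample size of 80 was calculated" for a MANOVA, and "an attrition rate of 35% was added based on a previous study", which gives 108.
- **Measurements.** Under Procedure, the outcomes (trait mindfulness, perceived stress, cortisol, CRP) are taken at the educational session before training starts, and again the morning after session 5.
- **Tests.** Under Statistical Analysis, "one-way MANOVA was used to test the study hypotheses". Post hoc one-way ANOVAs follow for each outcome at .0125. No baseline covariate, change score or time factor is mentioned. Baseline t-tests and chi-squared tests serve only to check the randomisation.
- **Missing data.** The whole provision is that "the data were examined for outliers, missing data, and violations of statistical tests assumptions and managed as appropriate". No analysis population, imputation or likelihood method, or sensitivity analysis is named.

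**The concern.** A one-way test has one factor, the study group. As written, the baseline values play no part in the comparison, although students lost later should have them.

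The plan expects heavy loss. Students may stop at any time, one arm learns a technique and the other sits with eyes closed, so different kinds of student could leave each arm. If, say, the more stressed leave one arm but not the other, the remaining groups already differ at baseline. An unadjusted comparison carries part of that difference into the result and can create or hide an effect. The randomisation checks do not correct for loss that comes afterwards.

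A MANOVA also needs all four outcomes on each person. Unless gaps are filled, a student with both questionnaires but no blood result drops out of the joint test.

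**Working it through.** **1. The plan's own figures.** Inputs from Sample Size Calculation: alpha .05, power 0.95, "number of dependent variables of 4, number of groups of 2", effect size 0.25. Reading 0.25 as f²(V), the test has df1 = 4, df2 = N − 5 and noncentrality 0.25 × N. The smallest N with power 0.95 is 80 (power 0.952), so 80 reproduces. The final size reproduces as 80 × 1.35 = 108. If 35% are lost, 108 × 0.65 = 70.2 remain, and power at N = 70 is 0.917. The loss of power is modest; the issue here is bias.

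**2. Assumptions, none of them in the documents.** 108/2 = 54 per arm; 35% lost in each arm; no true effect; baseline and follow-up standardised with correlation ρ from 0.3 to 0.7; loss follows a logistic model in baseline with slope b (log-odds per SD), its intercept set to give 35%.

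**3. Bias by formula.** Let s be the shift in mean baseline among an arm's completers. Integrating the logistic model over a standard normal baseline gives |s| = 0.166 for b = 0.5 and 0.292 for b = 1.0. Let Δ be the difference in s between arms. In absolute value:

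- follow-up values: bias = ρ × Δ
- change scores: bias = (1 − ρ) × Δ
- baseline-adjusted: bias = 0, because loss depends only on baseline and the regression is linear

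Loss related to baseline in one arm, b = 0.5, ρ = 0.3: 0.3 × 0.166 = 0.05. Same with b = 1.0, ρ = 0.7: 0.7 × 0.292 = 0.20. Opposite directions, b = 0.5: Δ = 2 × 0.166 = 0.332, giving 0.3 × 0.332 = 0.10 and 0.7 × 0.332 = 0.23.

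**4. False-positive rate by simulation.** 4,000 runs per setting, two-sided test of a single outcome at .0125, completers only; Monte Carlo standard error about 0.002 at the nominal rate. Bias is from step 3, in SD.

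| Loss depends on baseline | ρ | Follow-up: bias, rate | Change: bias, rate | Adjusted: rate |
|---|---|---|---|---|
| One arm, b = 0.5 | 0.3 | 0.05, 0.015 | 0.12, 0.017 | 0.013 |
| One arm, b = 0.5 | 0.7 | 0.12, 0.024 | 0.05, 0.015 | 0.011 |
| One arm, b = 1.0 | 0.3 | 0.09, 0.022 | 0.20, 0.038 | 0.013 |
| One arm, b = 1.0 | 0.7 | 0.20, 0.051 | 0.09, 0.019 | 0.011 |
| Opposite, b = 0.5 | 0.3 | 0.10, 0.018 | 0.23, 0.045 | 0.011 |
| Opposite, b = 0.5 | 0.7 | 0.23, 0.063 | 0.10, 0.027 | 0.012 |
| Same in both arms, b = 0.5 or 1.0 | 0.3 to 0.7 | 0, 0.009 to 0.015 | 0, 0.011 to 0.014 | 0.011 to 0.014 |

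Simulated bias of the adjusted estimate was 0.005 SD or less throughout. Loss was 35% in both arms in every row, so equal dropout rates do not protect the comparison. What matters is whether the kind of student who leaves differs by arm.

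**The case against.** The strongest reply is that the bias is assumed. The control condition is matched for time, attention, trainer contact and setting, the design is called blinded, and nothing in the documents shows that different students would leave each arm. If the mechanism is the same, there is no bias. This stands, and it makes the finding conditional.

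A reader might also infer four stronger points that the documents do not support:

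- **That the MANOVA is the only test.** The ANOVAs are stated too. Run separately, each loses only students missing that outcome. They still exclude every dropout and use no baseline.
- **That the plan prescribes listwise deletion or a follow-up-only comparison.** It states neither. The missing-data sentence leaves imputation open, and the score entering the MANOVA is not specified. But nothing is named that would fill gaps, and the table shows that change scores do not remove the problem.
- **That many students will lose questionnaire data through missed blood samples.** The same assistants collect both, blood first, so absence would usually remove both. No count can be derived.
- **That the .0125 level is broken.** At the mild end the rate is 0.015. The rates are for a single test; if the ANOVAs follow only a significant MANOVA, they are upper limits.

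Finally, the simulated gain comes from baseline adjustment among completers. It is not evidence that imputation or a mixed model would do better than that.

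**Conclusion.** The concern holds as a conditional weakness with a cheap remedy. The plan expects 35% attrition, collects baseline values on all four outcomes, and leaves them out of the tests it states.

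Under loss that depends on baseline differently by arm, the unadjusted comparison is off by roughly 0.05 to 0.23 SD. For scale, f²(V) = 0.25 with two equal groups is a multivariate distance D with D²/4 = 0.25, so D = 1. Spread evenly over four uncorrelated outcomes (an assumption), that is √(1/4) = 0.5 SD each. The bias would then be about a tenth (0.05/0.5) to just under half (0.23/0.5) of the planned effect.

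The actual size and direction cannot be worked out from the documents. Adjustment removes the bias only where loss depends on baseline; loss driven by the unseen outcome itself would remain.

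**What to change.** 1. **Put baseline into the main analysis.** Use a MANCOVA with the baseline values as covariates, followed by an ANCOVA for each outcome at .0125. The equivalent alternative is a mixed model of baseline and follow-up values for each outcome, with a common baseline mean.
2. **Name the analysis set.** Include all randomised participants with available data, in the arm assigned. Fit the per-outcome models separately, so that a missing blood sample does not remove the questionnaire outcomes. The MANCOVA itself still needs all four outcomes; say so, and report the number in each model.
3. **Sensitivity analyses.** Keep the unadjusted complete-case MANOVA, and add one delta-shift analysis in which the unobserved outcomes of dropouts are made worse.
4. **Report attrition by arm**, with baseline values of completers and dropouts.

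The cost is a few hours of analysis, with no new data. The main analysis rests on a missing-at-random assumption, which the delta-shift analysis probes. The MANCOVA keeps the multivariate structure behind the sample size. Adjustment also helps precision without any dropout: at ρ = 0.3 to 0.7, residual variance falls by ρ², that is 9% to 49%.
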